## 4. Explanation and Informed Consent

### 4.1 Preparation of Written Information and Informed Consent Form

The investigator will prepare written information and the informed consent form. The informed consent form and written information will consist of either a unified document or a set of documents. The document will be revised, as necessary.

The prepared and revised documents shall be submitted to the sponsor and approved by the institutional review board (IRB) prior to initiation of the study.

### 4.2 Contents of the Written Information

The written information for subjects should include explanations regarding the following:

- (1) That the study involves research.
- (2) The purpose of the study.
- (3) The name, title, and contact information of the investigator or subinvestigator.
- (4) Study methods (including aspects of the study that are experimental, inclusion criteria, and the probability for random assignment to each treatment).
- (5) That there is no intended benefit of the study drug on the subject's mental and physical health, and foreseeable inconvenience to the subject.
- (6) The expected duration of the subject's participation in the study.
- (7) That the subject's participation in the study is voluntary and that the subject may refuse to participate or withdraw from the study, at any time, without penalty or loss of benefits to which the subject is otherwise entitled.
- (8) That the monitor(s), auditor(s), IRB, and regulatory authority(ies) will be granted direct access to the subject's original medical records and data, without violating the confidentiality of the subject, to the extent permitted by applicable laws and regulations and that, by signing a written informed consent form, the subject is authorizing such access.
- (9) If the results of the study are published, the subject's identity will remain confidential.
- (10) The person(s) to contact for further information regarding the study and the rights of study subjects, and whom to contact in the event of a study-related injury.
- (11) The compensation and treatment available to the subject in the event of a study-related injury.
- (12) The type of IRB that reviews and discusses the appropriateness of the concerned study, the matters to be reviewed and discussed at the IRB, and other study-related issues for the IRB.
- (13) The approximate number of subjects involved in the study.
- (14) That the subject will be informed in a timely manner if information becomes available that may be relevant to the subject's willingness to continue participation in the study.
- (15) The foreseeable circumstances and reasons under which the subject's participation in the study may be terminated.
- (16) The anticipated expenses, if any, to the subject for participating in the study.

- (17) The anticipated prorated payment, if any, to the subject for participating in the study (including the calculation method of the payment).
- (18) The subject's responsibilities.

#### **4.3 Methods of Obtaining Informed Consent**

- (1) Prior to the start of the study, the investigator (or subinvestigator) will provide each prospective subject with an informed consent form and written information approved by the IRB, as well as a thorough explanation regarding the study. Study collaborators can also give supplementary explanations to prospective subjects. The explanation provided to the prospective subjects should be expressed in plain words and expressions, whenever possible so that he/she can easily understand the information. Each prospective subject must be given ample opportunity to inquire about the details of the study and receive answers to his/her satisfaction. The investigator (or subinvestigator) will obtain written consent to participate in the study from each prospective subject at his/her free will, after acquiring a thorough understanding.
- (2) In the informed consent form, the investigator (or subinvestigator) who has provided an explanation and the prospective subject should sign or affix their name and seal with the date of entry. If a study collaborator has provided a supplementary explanation, he/she should also sign or affix his/her name and seal to the form with the date of entry.
- (3) Prior to each subject's participation in the study (screening), the investigator (or subinvestigator) will issue a copy of the signed or named and sealed informed consent form with the date of entry, together with written information to the subject and retain the original, in accordance with the rules at the study site.
- (4) The investigator (or subinvestigator) will record the date of consent and the version of the informed consent form and written information used for explanation in each subject's case report form (CRF).

#### **4.4 Revision of the Informed Consent Form and Written Information**

- (1) When any new and important information is obtained that may affect the consent of the subjects, the investigator (or subinvestigator) shall immediately provide the subjects with such information orally, confirm the intention of the subjects to continue participation in the study, and record the results in the medical records.
- (2) Based on the information, the investigator will promptly judge whether it is necessary to revise the informed consent form and written information.
- (3) When the investigator judges it necessary to revise the informed consent form and written information, he/she shall immediately perform these revisions and obtain approval from the IRB.
- (4) The investigator (or subinvestigator) will inform the subjects undergoing the study of such information using the informed consent form and written information that has

been newly-approved by the IRB, and obtain a freely given written consent from each subject to continue participation in the study.

- (5) In the same manner as the first consent, the investigator (or subinvestigator) who has provided an explanation and the subject will sign or affix their name and seal with the date of entry. If a study collaborator has provided a supplementary explanation, he/she should sign or affix his/her name and seal to the form with the date of entry.
- (6) The investigator (or subinvestigator) will issue a copy of the signed or named and sealed informed consent form with the date of entry, together with written information to the subject and retain the original, in accordance with the rules at the study site.
- (7) The investigator (or subinvestigator) will record the date of consent and the version of the informed consent form and written information used for explanation in the CRF.

## 5. Study Design

### 5.1 Phase and Type of the Study

Phase of the study : I

Type of study : Clinical pharmacology study

### 5.2 Study Design

This study will be performed using a placebo-controlled, randomized, single-blind design, and consists of Part 1 (single-dose study) and Part 2 (multiple-dose study).

The flow of cohort transition in this study is shown in Figure 1. Except in Cohorts S3-1 and S3-2, no subjects will be administered the study drug in multiple cohorts.

[figure not shown]

Figure 1 Cohort Transition Flow

### 5.3 Methods of Blinding and Randomization

#### 5.3.1 Blinding Methods

This study will be performed using a single-blind design, in which the subjects are kept unaware of their assignments.

Prior to allocation of the study drugs, the randomization manager will confirm that the investigational drug and its comparator are indistinguishable in appearance of the solution and suspension, respectively. The randomization manager will record and report this indistinguishability to the sponsor in writing. More detailed blinding methods are specified in the separately prepared Procedures for Study Drug Assignment.

### **5.3.2 Methods of Randomization and Allocation**

The study drug allocation manager will assign drug numbers to the study drugs according to the randomization code list prepared in advance by the randomization manager. The investigator will administer the study drug bearing the drug number that corresponds to the subject ID code. The randomization manager will properly store and manage the randomization code list and submit a copy of the randomization code list to the sponsor. The subjects will be prescribed the study drug under blinded conditions. The investigator (or subinvestigator) will record the drug number in the CRF.

More detailed randomization methods are specified in the Procedures for Study Drug Assignment.

## **5.4 Endpoints**

### **5.4.1 Safety Endpoints**

- (1) AEs and ADRs
- (2) 12-lead ECG
- (3) Vital signs
- (4) Laboratory tests
- (5) Sensory tests

**[Rationales for setting]**

The above parameters were established to assess the safety of the study drug.

### **5.4.2 Pharmacokinetic Endpoints**

- (1) Plasma drug concentrations  
Unchanged edaravone, sulfate conjugate, and glucuronide conjugate
- (2) PK parameters  
 $AUC_{0-\text{last}}$ ,  $AUC_{0-12\text{hr}}$ ,  $AUC_{0-24\text{hr}}$ ,  $AUC_{0-\infty}$ ,  $C_{\max}$ ,  $C_{\text{trough}}$ ,  $t_{\max}$ ,  $t_{1/2}$ ,  $\lambda_z$ ,  $MRT^*$ ,  $CL/F^*$ ,  $V_z/F^*$ , and  $V_{ss}/F^*$  (\*: calculated for unchanged edaravone only)

**[Rationales for setting]**

Based on changes in plasma drug concentrations, the PK parameters will be calculated to characterize the PK profiles in healthy adult males.

### **5.4.3 Pharmacodynamic Endpoints**

Heart rate, QTcF, PR interval, QT interval, RR interval, and QRS interval from Holter ECG

**[Rationales for setting]**

To evaluate QTcF prolongation and proarrhythmic potential for edaravone.

## **6. Sample Size and Planned Study Period**

### **6.1 Sample Size**

A total of 74 subjects

Part 1 (single-dose study): 56 subjects (8 subjects per cohort: 6 subjects in the edaravone group and 2 subjects in the placebo group)

Part 2 (multiple-dose study): 18 subjects (9 subjects per cohort: 6 subjects in the edaravone group and 3 subjects in the placebo group)

[Rationales for setting]

Although the target sample size is not based on a power calculation, it is considered appropriate for the collection of results to meet the study objectives.

### **6.2 Planned Study Period**

From March 2018 to September 2018

## 7. Study Drug

### 7.1 Name of the Study Drug

#### (1) Investigational drug

Name: Edaravone powder

Description: White to pale yellowish white crystals or crystalline powder

#### (2) Comparator

Name: Crystalline cellulose powder

Description: White crystalline powder

The study site will prepare an oral solution or suspension of the investigational drug and comparator before use. Detailed preparation methods are specified in a separate procedure. The study site will purchase the purified water, polyvinyl alcohol (Japanese Pharmaceutical Excipient), and xanthan gum (Japanese Pharmaceutical Excipient) needed for preparation.

#### Investigational drug:

Edaravone powder will be dissolved or suspended in polyvinyl alcohol (Japanese Pharmaceutical Excipient) or a mixture of polyvinyl alcohol (Japanese Pharmaceutical Excipient) and xanthan gum (Japanese Pharmaceutical Excipient), and used as an oral solution or suspension.

- Cohorts S1, S2, S3, S5, S6, S7, M1, and M2: Polyvinyl alcohol
- Cohort S4: Polyvinyl alcohol and xanthan gum

#### Comparator:

##### 1) Comparator to the solution

For Cohort S1, dissolve polyvinyl alcohol (Japanese Pharmaceutical Excipient) in purified water, and use the mixture as an oral solution.

##### 2) Comparator to the suspension

Suspend crystalline cellulose powder in polyvinyl alcohol (Japanese Pharmaceutical Excipient) or in a mixture of polyvinyl alcohol (Japanese Pharmaceutical Excipient) and xanthan gum (Japanese Pharmaceutical Excipient), and use the mixture as an oral suspension.

- Cohorts S2, S3, S5, S6, S7, M1, and M2: Polyvinyl alcohol
- Cohort S4: Polyvinyl alcohol and xanthan gum

If the dosage form of the investigational drug (solution or suspension) is changed, the same dosage form will be used for the comparator.

### 7.2 Packaging and Labeling of the Study Drug

The study drug, packed in duplicate polyethylene bags will be placed in a fiber drum when being supplied to the study site. The packaging should bear the intended use (i.e., for the

clinical study), name and address of the sponsor, chemical name or identification mark, lot number, and storage conditions.

### **7.3 Storage Conditions**

Storage at room temperature

### **7.4 Handling, Storage, and Management Methods of the Study Drug**

After concluding a study contract with the study site, the sponsor will supply the study drug. The study drug manager will store and manage the study drug in accordance with the "Study Drug Management Procedures" established by the sponsor and, after the end of the study, he/she will return all used study drugs to the sponsor.

The study drug must be used only for the purposes specified in the protocol (and must not be used for other purposes, such as other clinical studies, animal studies, or basic experiments).

## **8. Study Methods Related to Subjects**

### **8.1 Preparation of Subject Screening and Enrollment Logs and List of Subject ID Codes**

The investigator will prepare a subject screening log that includes all of the prospective subjects who have undergone screening (and received explanation of the study). Of these subjects, those who have provided informed consent will be given a subject ID code, and the investigator will prepare a list of subject ID codes. At that time, the investigator will also include key information that allows the verification of source data.

In addition, the investigator will prepare a subject enrollment log with such information as the date of consent and subject ID code of all of the subjects who are enrolled in the study (including those who have interrupted or discontinued the study).

The investigator will provide the sponsor with the subject screening log, as requested by the sponsor, while ensuring the appropriate protection of the subjects' privacy and confidentiality.

### **8.2 Subject Enrollment**

After closing the contract between the study site and the sponsor, and the start of the study period specified in the contract, the investigator (or subinvestigator) will conduct the observations and tests (see "9. Tests and Observations") for subjects who have provided written informed consent within 30 days before starting administration of the study drug. The study drug will be administered to subjects who meet all of the inclusion criteria and none of the exclusion criteria. If any abnormal finding is detected in any subject during the observations and tests prior to the start of the study drug administration, that subject will be examined from a medical point of view to ensure the safety of the subject and to examine whether there is no concern regarding the safety assessment of the study drug. If a retest is required to make a medical judgment, the test will be performed after an appropriate interval. If the finding is judged to be of no concern from a medical point of view, the investigator (or subinvestigator) will record the reason for the judgment in the source data and administer the study drug to the subject. If any subject is excluded due to ineligibility prior to study drug administration, the investigator (or subinvestigator) will record the reasons in the subject screening log, and replace the excluded subject with a reserve subject.

#### **8.2.1 Replacement of Subjects**

Except for Cohort S3-2, the study site will keep one or more reserve subjects in addition to the planned number of subjects, from the eligible volunteers who have passed the screening, to allow for subject replacement after hospitalization and prior to administration. In case of subject replacement immediately before administration, the study drug assigned to the original subject will be given to the replacement subject. In the case of subject replacement before administration, a replaced subject who did not receive the study drug will not be handed as a withdrawal or dropout. If there are an insufficient number of reserve subjects and

the target number of subjects is not reached before administration, the investigator will have a discussion with the sponsor about the enrollment of new subjects. If it is determined to be necessary in the discussion, additional subject(s) will be enrolled to continue the study.

After administration, any withdrawals or dropouts will not be replaced. In Cohorts S3-1 and S3-2, the same subjects will be enrolled; therefore, if any subject is excluded from Cohort S3-2 due to being judged as ineligible before the administration, he will be handled as a withdrawal/dropout, and will not be replaced.

### 8.3 Dose and Dosing Regimen

#### 8.3.1 Dose, Dosing Regimen, and Duration of Administration

The dose, dosing regimen, and duration of administration for each cohort of Parts 1 and 2 are shown in the table below. Detailed administration procedures are specified in the separately prepared Procedures for Cohort Transition.

Except in Cohorts S3-1 and S3-2, no subjects will be administered the study drug in multiple cohorts.

##### (1) Part 1 (single-dose study)

A single oral dose of the study drug will be given to subjects under fasting conditions in the morning or 30 minutes after breakfast. In Cohort S3-2, subjects in Cohort S3-1 will be given the same study drug that is allocated in Cohort S3-1 in a single oral dose after at least a 4-day washout period. Doses of Cohort S2 and thereafter are tentative. Based on the PK data obtained up to 24 hours post-dose and the safety data obtained up to 48 hours post-dose of the previous cohort, the sponsor and a medical expert will examine and determine the dose with the agreement of the investigator, such that the exposure of the minimum toxic dose (10,226 ng/mL for  $C_{max}$  and 1,226 ng•hr/mL for  $AUC_{0-24hr}$  in a free base form) is not exceeded. However, the highest dose in Part 1 shall not exceed 7,200 mg. The common ratio between the dose and the estimated mean  $C_{max}$  and  $AUC_{0-24hr}$  should be  $\leq 5$  between successive cohorts.

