## **5.2 Dose, Dosing Regimen, and Duration of Administration**

The dose, dosing regimen, and duration of administration for each cohort of Parts 1 and 2 are shown in the table below.

Except in Cohorts S3-1 and S3-2, no subjects will be administered the study drug in multiple cohorts.

(1) Part 1 (single-dose study)

A single oral dose of the study drug will be given to subjects under fasting conditions in the morning or 30 minutes after breakfast. In Cohort S3-2, subjects in Cohort S3-1 will be given the same study drug that is allocated in Cohort S3-1 in a single oral dose after at least a 4-day washout period. Doses of Cohort S2 and thereafter are tentative. Based on the PK data obtained up to 24 hours post-dose and the safety data obtained up to 48 hours post-dose of the previous cohort, the sponsor and a medical expert will examine and determine the dose with the agreement of the investigator, such that the exposure of the minimum toxic dose (10,226 ng/mL for  $C_{max}$  and 1,226 ng•hr/mL for  $AUC_{0-24hr}$  in a free base form) is not exceeded. However, the highest dose in Part 1 shall not exceed

7,200 mg. The common ratio between the dose and the estimated mean  $C_{max}$  or  $AUC_{0-24hr}$  should be  $\leq 5$  between successive cohorts.

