**[Rationales for setting]**

Administration under fasting conditions was selected to avoid the effect of food on the PK parameters. Only at an estimated clinical dose of 800 mg, administration under fasted and fed conditions was established to examine the effect of food on the PK parameters.

The initial dose in the single-dose study was determined as described below. Based on the NOAEL of 10 mg/kg (through the IV route in rats) and 30 mg/kg (through the oral route in dogs), a human equivalent dose was calculated and divided by a safety factor of 10. As a result, the recommended maximum initial dose (at a body weight of 60 kg) was determined as 9.7 mg (through the IV route) and 100 mg (through the oral route). As the already approved IV dose is 60 mg per day, the initial oral dose was determined as 60 mg.

The highest dose was established not to exceed the exposure (10,226 ng/mL for  $C_{max}$  and 1,226 ng•hr/mL for  $AUC_{0-24hr}$  in a free base form) at the minimum toxic dose (30 mg/kg by the IV route) in rats that showed the highest sensitivity in the repeat-dose toxicity studies. The estimated  $AUC_{0-24hr}$  at the highest dose is as high as close to the  $AUC_{0-24hr}$  at the minimum toxic dose. Nevertheless, in a previous clinical study outside of Japan, an exposure of 1,886 ng•hr/mL for  $AUC_{0-24hr}$  (in a free base form) was observed in a subject receiving IV infusion, which exceeded the AUC at the minimum toxic dose. In that study, the commonly observed AEs were infusion site pain, diarrhoea, and headache, all of which were both reversible and also reported in the placebo group. Therefore, it was judged that the exposure raises no safety concerns.

The bioavailability (BA) of oral edaravone is estimated as 12%, based on the results of clinical studies of IV administration and an *in vitro* membrane permeability experiment. The highest possible dose was established as 7,200 mg, since if a dose  $\geq$ 7,200 mg were required as the highest dose, the calculated BA would be as low as <6%. In that case, it would be necessary to reconsider the development of this dosage form.

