The estimated PK parameters of oral edaravone in humans at the initial dose of 60 mg and the planned highest dose of 3,600 mg are as follows: 93 ng/mL for  $C_{max}$  and 202 ng•hr/mL for  $AUC_{0-24hr}$  at 60 mg (8 ng/mL for  $C_{max}$  and 16 ng•hr/mL for  $AUC_{0-24hr}$  in a free base form) and 5,577 ng/mL for  $C_{max}$  and 12,110 ng•hr/mL for  $AUC_{0-24hr}$  at 3,600 mg (452 ng/mL for  $C_{max}$  and 981 ng•hr/mL for  $AUC_{0-24hr}$  in a free base form).

Based on findings from the non-clinical studies, the estimated AEs are sedation, decreased blood pressure, and increased heart rate, which were transient in the studies. By observing the subjects' clinical symptoms and vital signs during the study period, it was determined to be feasible to conduct this study.

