#### **8.4 Judgment of Cohort Transition and Dose Change**

##### **(1) Part 1 (single-dose study)**

Upon finishing one cohort, the investigator will submit the "Results of Safety Evaluation up to 48 Hours Post-dose (During Hospitalization)" and "Investigator's View on Transition to the Next Cohort" to the sponsor in about 3 working days.

Based on the "Results of Safety Evaluation up to 48 Hours Post-dose (During Hospitalization)," "Investigator's View on Transition to the Next Cohort," and "Plasma Unchanged Drug Concentrations up to 24 Hours Post-dose\*," the sponsor will hold discussions with the medical expert, and obtain the "Medical Expert's View on Transition to the Next Cohort." Upon reaching a determination on whether or not to transit to the next cohort, along with the dose, the sponsor will prepare the "Notification of Transition to the Next Cohort and Dosing Regimen," and submit the form to the investigator with the "Plasma Unchanged Drug Concentrations up to 24 Hours Post-dose.\*" The investigator will inform the sponsor regarding whether or not he/she agrees with the above sponsor's

view using the "Cohort Transition Agreement Record," along with the reason if he/she disagrees. If the investigator's agreement is obtained, the sponsor will instruct to transit to the next cohort. If the investigator disagrees, the sponsor will hold discussions with the investigator until an agreement has been reached. Upon reaching an agreement, the sponsor will either instruct to transit to the next cohort with a determined dose or discontinue the study.

\*: The report includes a list of plasma unchanged drug concentrations,  $C_{max}$ , and AUC by subject.

(2) Part 2 (multiple-dose study)

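### The limit on escalation steps reads Cmax *or* AUC0-24hr in the Protocol Summary but Cmax *and* AUC0-24hr in the body, in both Parts

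*Protocol*

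**What the plan says.** Two numeric exposure rules govern dose selection.

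**Step limit.** It is stated four times. Each statement opens with "The common ratio between the dose and the estimated mean", names Cmax and AUC0-24hr, sets the limit at 5 or less and closes by referring to successive cohorts.

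| Place | Part | Wording |
|---|---|---|
| Protocol Summary 5.2 (1) | 1 | "estimated mean $C_{max}$ or $AUC_{0-24hr}$ should be" |
| Protocol Summary 5.2 (2) | 2 | same, with *or* |
| Section 8.3.1 (1) | 1 | "estimated mean $C_{max}$ and $AUC_{0-24hr}$ should be" |
| Section 8.3.1 (2) | 2 | same, with *and* |

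**Ceiling.** In Summary 5.2 (1) and Section 8.3.1 (1), the dose is chosen "such that the exposure of the minimum toxic dose" (free-form Cmax 10,226 ng/mL and AUC0-24hr 1,226 ng•hr/mL) is not exceeded. Neither place names a summary measure. The rationale in 8.3.1 (1) says the estimated AUC0-24hr "at the highest dose is as high as close to the" AUC at the minimum toxic dose. It then gives "The estimated PK parameters of oral edaravone in humans at the initial dose of 60 mg and the planned highest dose of 3,600 mg", one value per measure and dose.

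Doses from Cohort S2 on are tentative and are set from the PK and safety data of the preceding cohort.

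**The concern.** The step limit is an operative threshold that the sponsor and the medical expert apply, with the investigator's agreement, before each new cohort. Under *and*, the estimated mean Cmax and the estimated mean AUC0-24hr must both stay within a 5-fold increase. Under *or*, read permissively, it is enough that one does. A step with a 4-fold rise in Cmax and a more than 5-fold rise in AUC then passes under the Summary and fails under Section 8.3.1. Two parties could each follow a passage of the same protocol and reach different decisions on the same PK report.

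The ceiling sentence raises a smaller question. The step limit is expressly about an estimated mean, while the ceiling does not say whose exposure it limits.

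**Working it through.** **1. Reproduce the protocol's predictions** (8.3.1 (1) rationale: 60 mg gives Cmax 93 and AUC 202; 3,600 mg gives 5,577 and 12,110).

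- Dose ratio: 3,600/60 = 60.0
- Cmax ratio: 5,577/93 = 59.97
- AUC ratio: 12,110/202 = 59.95
- Free AUC at 3,600 mg: 12,110 × 0.081 = 981, as stated. The free fraction of 0.081 lies within the 8–9% implied by the 91–92% protein binding in Section 1.3.1.

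The predictions are dose-proportional for both measures, so the dose, Cmax and AUC ratios coincide at every step.

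**2. Planned steps against the limit of 5.** If exposure is proportional to dose^b, the exposure ratio for a dose ratio r is r^b. It exceeds 5 when b > ln 5 / ln r.

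| Step | Dose ratio r | Headroom 5/r | Exponent b needed |
|---|---|---|---|
| S1 to S2, 60 to 240 mg | 4.00 | 1.25 | 1.16 |
| S2 to S3-1, 240 to 800 mg | 3.33 | 1.50 | 1.34 |
| S3-1 to S4, 800 to 1,600 mg | 2.00 | 2.50 | 2.32 |
| S4 to S5, 1,600 to 2,400 mg | 1.50 | 3.33 | 3.97 |
| S5 to S6, 2,400 to 3,600 mg | 1.50 | 3.33 | 3.97 |
| M1 to M2, 800 to 2,400 mg/day | 3.00 | 1.67 | 1.46 |

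With b = 1 for both measures, every planned step complies under both wordings.

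**3. When the wordings part.** One measure must exceed 5 while the other does not. Take Cmax proportional and AUC with exponent b:

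- b = 1.1: the largest permitted dose step is 5^(1/1.1) = 4.32-fold under *and*, and 5-fold under *or*. The planned 4.0-fold step still passes both.
- b = 1.2: the 60 to 240 mg step gives AUC 4^1.2 = 5.28-fold and Cmax 4.0-fold. It fails under *and* and passes under permissive *or*.

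Because the doses are tentative, a revised step could be larger than the planned one. At a full 5-fold dose step, any exponent above 1 in one measure alone parts the wordings.

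**4. The ceiling.** 981/1,226 = 0.80, so a predicted mean of 981 complies, while a single subject 25% above that mean (1,226/981 = 1.25) would not. The protocol gives no between-subject CV. As an assumption, take log-normal AUC with arithmetic mean 981: s = √ln(1+CV²), median = 981/√(1+CV²), p = 1 − Φ(ln(1,226/median)/s), and the chance that at least 1 of 6 is above is 1 − (1−p)^6. At 2,400 mg the mean is scaled by 2,400/3,600.

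| Assumed CV | At 3,600 mg | At 2,400 mg |
|---|---|---|
| 10% | 6.5% | about 0% |
| 20% | 50% | 0.3% |
| 30% | 70% | 6.5% |
| 40% | 78% | 19% |
| 50% | 81% | 30% |

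The choice of reading therefore matters mainly near the planned top dose, and its size depends on an assumed CV.

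**The case against.** **The step limit is clear enough.** All four statements refer to successive cohorts and name dose, estimated mean Cmax and estimated mean AUC0-24hr. A reader might infer from the clumsy opening that a dose-to-exposure ratio is meant; the closing words rule that out. *Or* can also be read as saying that neither measure may exceed 5, which is the same as *and*. This stands as a possible reading, but the Summary does not say so, and the conflict with the body remains.

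**Nothing changes on the planned doses.** This stands. A reader might infer that the two wordings already permit different planned doses. The protocol's figures do not show that: no planned step exceeds 4.0-fold and the predictions are proportional.

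**The ceiling is settled by context.** This largely stands. The rationale sets one estimated exposure at the highest dose against the limit, and 981 against 1,226 fits an estimated mean. A reader might infer that the ceiling binds each subject and would be broken in most cohorts. The documents do not support that: the probabilities rest on an assumed CV and apply near 3,600 mg, in a tentative cohort. Nor does the protocol claim that no subject will exceed the limit. It discusses an AUC of 1,886 that "was observed in a subject receiving IV infusion, which exceeded the AUC at the minimum toxic dose". Even that single-subject cue is weak, since 22,455.6 (the dose-group AUC in Section 1.3.2) × 0.084 = 1,886, with 0.084 an assumed free fraction inside the 8–9% range.

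**Other safeguards apply.** Transition needs documented agreement, and "The report includes a list of plasma unchanged drug concentrations", with Cmax and AUC by subject, so any exceedance would be visible. The 7,200 mg cap and the stopping criteria also hold. These limit the consequences but do not say which wording governs. The Procedures for Cohort Transition (Appendix 3) are not shown and might clarify application; they would not remove the conflict between Summary and body.

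**Conclusion.** The step limit contradicts itself between Protocol Summary 5.2 and Section 8.3.1, in both Parts, and should be corrected because it is an operative dose-selection threshold. The practical effect is conditional: none on the planned doses under proportional PK, and a different decision only if the Cmax and AUC ratios fall on opposite sides of 5. For the steps with least headroom that needs an exponent above about 1.16, 1.34 or 1.46 in one measure alone. These thresholds assume a power relation between dose and exposure and the tentative doses as listed.

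The unnamed summary measure in the ceiling is a secondary clarification. The rationale points towards an estimated exposure at the dose, and this would not be a finding on its own.

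**What to change.** - Reconcile Summary 5.2 (1) and (2) and Section 8.3.1 (1) and (2) to one sentence. It should state which next-to-previous-cohort ratios are limited (dose, estimated mean Cmax, estimated mean AUC0-24hr) and whether all of them must comply.
- In the same edit, state in Summary 5.2 (1) and Section 8.3.1 (1) whether the ceiling applies to the estimated cohort mean or to each subject, consistently with the planned highest dose. Table 1 note 4, which relies on the same ceiling, should follow that definition.
- Check that the Procedures for Cohort Transition use the same wording.

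The cost is text in a protocol revision, with no change to sample size, sampling or analysis. If the sponsor declares the ceiling to be per subject, the rationale for the planned highest dose would have to be reconciled with it. No limit, dose or clinical rule is proposed here.
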